1.5.2 Focused physical examination

Physical examination will be done at screening/baseline (before treatment), Day 1, Day 2, Day 3, Day 4, Month 1, Month 3, Month 6, Months 7-11, Month 12/EOS/ET. Normal, abnormal and clinically significant findings will be assessed.

1.5.3 Vital signs

Vital signs will be assessed from screening/baseline (before treatment), Day 1, Day 2, Day 3, Day 4, Month 1, Month 3, Month 6, Months 7-11, Month 12/EOS/ET. Vital signs endpoints include:

- Values collected at each visit
- Changes from baseline

1.5.4 Anti-drug Antibodies (ADA)

Blood samples will be taken for measurement of serum neutralizing antibody testing against QM1114-DP at baseline (before treatment), Month 1, and Month 6.

Analysis of the blood samples include in vitro screening and confirmatory (if positive screening result) ELISA assays to test for the presence of binding antibodies, and in vivo mouse protection assay (MPA) to test for the presence of neutralizing antibodies. The MPA will only be conducted if the subject has a positive confirmatory result. ADA categories outlined in [Section 2.5.3](#) will be determined based on the confirmatory assay results.

2 Statistical Methods

2.1 General methods

All tables, listings, and figures will be programmed using SAS Version 9.4 or higher. Data collected in this study will be documented using summary tables and subject data listings created by the SAS® system. Confidence intervals (CI) and p-values will be 2-sided and performed at a significance level of 5%, unless otherwise specified. Data for all subjects in the clinical database will be included in the data listings. Calculated (derived) variables will be listed as appropriate. Any changes from the SAP will be detailed in the clinical study report.

All efficacy, safety and baseline characteristics variables will be presented using descriptive statistics within each treatment group, and graphs as appropriate. Continuous variables will be summarized using descriptive statistics (n [number of observations], mean, standard deviation [SD], median, minimum, and maximum), unless otherwise specified. Categorical variables will be presented in frequency tables with number and percentage of observations for each level.

Study days will be calculated relative to the injection of study drug. Day 0 will be the day of study drug administration. Baseline will be the last assessment prior to the injection of study drug unless otherwise indicated. The Screening Visit 1 (Day -14 to Day 0) will be considered the visit prior to injection of study drug. Because the Screening visit and Baseline visit (Day 0) may be performed on the same day, the Screening visit can also be Day 0.

Adverse events, cosmetic/aesthetic procedures and implant history events, medical history events, previous neuromodulator treatments, and concomitant treatments/procedures will be coded using MedDRA, Version 25.0 or higher. Prior/concomitant medications and procedural anesthetics will be coded using the World Health Organization (WHO) Drug Dictionary Global, March 2022 B3 or higher.

In general, efficacy, safety, and exploratory analyses will be performed and summarized by treatment group (QM1114-DP, placebo), unless otherwise stated.

2.1.1 Visit windows

Study visits are expected to occur according to the protocol schedule of assessments in [Appendix A](#). All data will be tabulated per the evaluation visit as recorded on the eCRF even if the assessment is outside of the visit window. In data listings, the relative study day (in relation to date of study drug administration) of all dates will be presented. There will not be any windowing for unscheduled visits in the analysis, and unscheduled visits will not be included in any analyses. Unscheduled visits, if any, will be presented in listings only.

Measures to minimize the risk of exposure to COVID-19 for study subjects include, but are not limited to, replacing site visits with telephone call visits, replacing live assessments with remote digital assessments, postponing site visits and cancellation of site visits not needed for evaluation of primary endpoint.

2.1.2 Handling of Missing/Partial Dates

The handling of missing/partial dates for Adverse Events and Concomitant Medications/Procedures is outlined below. See [Section 2.4.2](#) for handling of missing data for the efficacy analyses.

While every effort will be made to obtain full, complete information on every reported medication, the following imputation rules will be followed for any respective missing medication data:

For the purpose of determining whether a medication is considered prior or concomitant, the following date imputation rules will be used. Dates will be presented as collected in the listings.

- Start Date
 - If the start date is completely missing, it will be assumed that the medication started on the study treatment date.
 - If the start date is missing the day, the first of the month will be used (i.e., UNK-JAN-2022 becomes 01-JAN-2022), provided the imputed date is on or after the subject's study treatment date; otherwise, the day of study treatment will be used.
 - If the start date is missing the month, the month of 'June' will be used (i.e., 01-UNK-2022 becomes 01-JUN-2022), provided the imputed date is on or after the subject's study treatment date; otherwise, the subsequent month after study treatment will be used.
 - If the start date is missing the year, the year of study treatment will be used (i.e., 01-JAN-UNK becomes 01-JAN-2022), provided the imputed date is on or after the subject's study treatment date; otherwise, the subsequent year after treatment will be used.
- End Date
 - If the end date is completely missing, it will be assumed that the medication is still ongoing and will not be imputed.
 - If the end date is missing the day, the last day of the month will be used (i.e., UNK-JAN-2022 becomes 31-JAN-2022).
 - If the end date is missing the month, the subsequent month after the start date will be used.
 - If the end date is missing the year, the year of study treatment will be used (i.e., 01-JAN-UNK becomes 01-JAN-2022), provided the imputed date is after the start date; otherwise, the subsequent year after start date will be used.

While every effort will be made to obtain full, complete information on every reported AE, the handling of any respective missing AE data will follow the rules above, but for adverse events. These rules will be used to calculate treatment emergence, onset time, and duration. Dates will be presented as collected in the listings.

2.2 Analysis Populations

The statistical analyses will be performed based on the following three subject populations:

- Intention-to-treat Population - The Intent-to-treat (ITT) population includes all subjects who are randomized and dispensed the investigational product and will be analyzed according to the randomization scheme.

- Per-protocol Population - The Per-protocol (PP) population includes the ITT subjects who complete the Month 1 visit and have no protocol deviations that are considered to have a substantial impact on the primary efficacy outcome.
- Safety Population - The safety population includes all subjects who were administered the study product and will be analyzed according to as-treated principle.

2.3 Study subjects

2.3.1 Subject disposition

Subject disposition will be presented by treatment group and overall. The number of subjects in each study population (i.e., ITT, PP and Safety) will be summarized. Study population variables will also be presented in a data listing. Study completion, as well as early discontinuation, randomization, and study visits will be presented in data listings for all subjects.

Reasons for early discontinuation will be summarized and listed. All withdrawn subjects will be listed individually, including at least subject number, date and reason for withdrawal, and last visit performed, along with the relevant comments recorded on the eCRF.

2.3.2 Protocol deviations

A protocol deviation occurs when a subject deviates from the protocol procedures. Depending on the seriousness of the deviation, the subject might be excluded from the Per-Protocol (PP) population, which will be documented prior to database lock. Protocol deviations will be summarized by study site and in total (by treatment group and overall). Since PP population will be used for the sensitivity analysis of the primary endpoint at Month 1 only, the focus will be on deviations occurring before and on Month 1 visit day, as they might compromise the primary endpoint.

For this study, the protocol deviations that will exclude subjects from PP population will be established pre-database lock, with the reasoning for exclusion documented. Protocol deviations that will exclude subjects from the PP population include, but are not limited to, deviations that impact the primary efficacy endpoint. Subjects excluded from the PP population will be presented in a data listing.

Before unblinding the subject data, and as a part of preparations for the database lock, the study team will review all protocol deviations. All protocol deviations will be presented in a data listing individually, including subject number and observed deviation.

2.3.2.1 Out of Window visit duration

When a subject performs a planned study visit outside of the protocol-specified visit windows ([Appendix A](#)), the subject has an out of window study visit, which is considered a type of protocol deviation for this study. Knowing a subjects Screening visit (Visit 1) and Baseline visit (Visit 2) and using the protocol-specified visit windowing, one can calculate a subject's target study visit window date range for each planned study visit. Then, by comparing a subject's actual study visit date to the target study visit window date range, one can calculate the days over/under the actual study visit in relation to the target study visit date, or study visit out of window duration.

The duration, in days, a study visit is out of window will be summarized by treatment group, overall, and by visit. Out of window visit durations will be presented by site as well. Duration will be split into the following below categories. Duration categories will include both days before and days after the target planned visit date.

- +/- 1-2 days
- +/- 3-7 days
- +/- 8-20 days
- +/- 21 or more days

The number and percentage of subjects within each out of window duration category will be presented descriptively. For the overall analysis, percentages will be calculated using the number of subjects with an out of window visit at the respective visit as the denominator; for the by site analysis, percentages will be calculated using the number of subjects at the respective site as the denominator.

2.3.3 Demographic characteristics

Demographic assessments for this study include:

- Age (years)
- Height (in)
- Weight (lbs.)
- Gender (Male, Female)
- Ethnicity (Hispanic or Latino, Not Hispanic or Latino)
- Race (White, Black or African American, Asian, American Indian or Alaska Native, Native Hawaiian or Other Pacific Islander, Other)
- Fitzpatrick Skin Type (FST) score (I, II, III, IV, V, VI)

Subject demographic data will be summarized for the ITT population by treatment group and overall. Age, height, and weight will be analyzed as continuous variables. Gender, race, ethnicity, and FST will be analyzed as categorical variables.

Demographics and baseline characteristics will be presented by subject in a data listing.

2.3.4 Medical History and Prior Cosmetic/Aesthetic Procedures or Implants

All summaries will be done by treatment group and overall based on the ITT population. History of relevant or clinically significant surgical events and medical conditions, including any prior cosmetic/aesthetic procedures or implants, will be collected. Medical History will be coded according to MedDRA; the version used will be noted as a footnote in the tables and listings.

The number and percentage (where the denominator is the number of subjects in the ITT population) of subjects reporting medical history will be summarized by system organ class (SOC) and preferred term (PT). System organ class and PTs will be presented in descending frequency first based on the QM1114-DP group, and then alphabetically if there are ties. Each subject will contribute at most one count per summarization category. In other words, if a subject has more than one medical history event with same PT, the subject will be counted only once for that PT.

Similarly, if a subject has more than one medical history event for a SOC, the subject will be counted only once in that SOC.

Cosmetic/aesthetic procedures and/or implant history will also be presented and will follow the same methods specified above.

Medical history, and prior cosmetic/aesthetic procedures or implants will be provided in the subject data listing.

2.3.5 Previous and Concomitant Procedures

All summaries will be done by treatment group and overall based on the ITT population.

Concomitant procedures/treatments are defined as any new procedures/treatments received by the subject prior to the date of injection. Concomitant procedures/treatments include those that had changes to existing therapies during the course of the study and those that are ongoing since the date of injection. Previous procedures/treatments are procedures/treatments with stop dates within 4 weeks prior to screening visit.

Previous and concomitant procedures/treatments will be coded according to MedDRA. Therapies and procedures that started due to a related AE will be summarized separately from those who did not start due to an AE. Previous and concomitant procedures/treatments will also be presented and will follow the same methods specified in [Section 2.3.4](#) for medical history.

The number and percent (where the denominator is the number of subjects in the ITT population) of subjects with previous neuromodulator treatment will be summarized by neuromodulator treatment and separately by treatment location.

Previous and concomitant procedures/treatments will be presented by subject in a data listing. Previous neuromodulator treatments will be presented in a separate listing.

2.3.6 Prior and Concomitant Medications

All summaries will be done by treatment group and overall based on the ITT population.

Concomitant medications for this study are defined as any ongoing medications with a start date prior to the date of injection, any changes to existing medications (such as dose or formulation) during the course of the study, or any new medications received by the subject since the date of injection. Prior medications are medications with stop dates prior to study treatment and used within 4 weeks preceding screening visit. Medications will be coded using the World Health Organization (WHO) Drug Dictionary. The versions used for the coding will be noted as a footnote in the tables and listings.

The number and percentage of subjects who receive prior and concomitant medications will be summarized by the WHO Drug Dictionary Anatomical Therapeutic Chemical 4th level (ATC-4) and the preferred name, where percentage is defined as the number of subjects who receive prior and concomitant medications divided by the number of subjects in the ITT population times 100. If the 4th level term is not available, the next available level (e.g., ATC-3) will be used. Medications that started due to a related AE will be summarized separately from those who did not start due to an AE.

In addition, the number and percentage of subjects reporting a concomitant medication/therapy will be summarized by reason administered (medical history, adverse event, concomitant procedure, contraception, or other), where percentage is defined as the number of subjects with a specific reason administered divided by the number of subjects who received concomitant medications times 100.

ATC-4 and preferred name will be presented in descending frequency first based on the QM1114-DP group, and then alphabetically if there are ties. Each subject will contribute at most one count per summarization category. In other words, if a subject has more than one medication with same preferred name, the subject will be counted only once for that preferred name. Similarly, if a subject has more than one medication for an ATC-4 level, the subject will be counted only once in that ATC-4 level and preferred name.

Prior and concomitant medications will be presented by subject in a data listing. For handling of missing/partial dates, please see [Section 2.1.3](#).

2.4 Efficacy analysis

2.4.1 Datasets analyzed

All primary efficacy, secondary efficacy and exploratory endpoints will be analyzed based on the ITT population, unless otherwise specified below. All primary efficacy, secondary efficacy and exploratory endpoints will be included in separate data listings.

2.4.2 Handling of missing data

In general, the number of subjects with missing values will be summarized and reported as appropriate in all outputs. The primary analysis will be performed using the result of 'No Change' for any missing Month 1 GAIS assessment as the primary imputation method.

In addition, to further evaluate the impact of missing data on the primary endpoint, additional sensitivity analyses will be performed:

1. The primary analysis will be repeated using multiple imputation (MI) based on the ITT population
2. The primary analysis will be repeated using Observed Cases (OC) based on the ITT population (i.e., no imputation will be done)

The secondary efficacy analyses, exploratory analyses and safety analyses will be performed using OC. If deemed necessary, any analyses may be repeated using OC, 'No Change' imputation, baseline observation carried forward (BOCF), or MI as appropriate. Calculations for the FACE-Q and FLTSQ will follow the methods specified in the manuals for the handling of the data.

Missing data for Month 1 GAIS responses will be imputed using the following steps:

1. The imputation using MI will assume the Missing Completely at Random (MCAR) missing data assumption. Regardless of the actual pattern of missing data, the Markov Chain Monte Carlo (MCMC) method of the MI procedure from the SAS® system will first be used to create a monotonic pattern of missing data. The minimum values for imputed variables will be set to 0, in order to force PROC MI to redraw another value for imputation when an intended imputed value is less than the 0. The maximum value for imputed variables will be

set to 6, in order to force PROC MI to redraw another value for imputation when an intended imputed value is greater than 6. Imputed values will be rounded to the nearest integer. The seed number to be used will be the number 110196.

2. Then, a second SAS PROC MI procedure will be used for imputing missing values of data with monotone missing pattern. Imputations will be made using the MCMC-imputed dataset from step one (1). A linear regression will be employed to model the missing GAIS scores with the following covariates included in each imputation model: treatment group and all non-missing GAIS scores from earlier scheduled time points, including baseline. The seed number to be used will be the number 110196 and five (5) sets of imputations will be created. The Month 1 GAIS responder variable will be calculated from the imputed GAIS values as detailed in [Section 1.3.1](#).
3. The imputed datasets will be analyzed as specified in [Section 2.4.3](#).
4. The results from the CMH analysis of the multiple imputed datasets will be combined using the Wilson-Hilferty transformation by Ratitch et al. [1] to produce a pooled CMH statistic and p-value. The differences in proportions and standard errors will be combined using the SAS PROC MIANALYZE. The resulting pooled difference and standard error will be used to produce the 95% CI based on the large-sample approximation method for binary data without using continuity correction.

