5. SELECTION AND DISPOSITION OF CLINICAL STUDY POPULATION

5.1 Number of Subjects

As a screen failure rate of approximately 10% is anticipated, approximately 134 subjects will be screened in order to get 120 subjects enrolled in a 3:1 ratio to QM1114-DP 50 U (N=90) or placebo (N=30). It is expected that each center will recruit a similar number of subjects.

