9.2 Sample Size Determination

The study is planned to enroll approximately 120 subjects who will be treated with either 50 U of QM1114-DP (90 subjects) or placebo (30 subjects).

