1.1.2 Number of subjects and randomization

The study will screen approximately 134 male and female adults, 18 years of age or older, with moderate to severe glabellar lines at maximum frown and previous treatments with BoNT-A products within the 3 years prior to screening visit. A total of approximately 120 subjects will be randomized and enrolled at least 5 study sites. Following the screening process, eligible subjects will be randomized at the baseline visit (Day 0) in a 3:1 ratio to QM1114-DP or placebo, stratified by site.

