1.3.1 Global Aesthetic Improvement Scale (GAIS)

The GAIS consists of seven ratings used to assess the aesthetic improvement of the GL at maximum frown relative to pre-treatment appearance. Subjects will be asked:

- *“How would you rate the change in appearance of your glabellar lines (lines between your eyebrows) at maximum frown compared with immediately before the injection?”*

Subjects will be instructed to select the one rating, using the below categorical scale ([Table 1](#)), that best describes the degree to which the appearance of their GLs at maximum frown has changed relative to baseline. Ratings will also be recoded with numeric values 0-6 (as seen in Table 1). The subject may review the baseline photograph to aid in the assessment.

Subjects will rate the global aesthetic improvement of their GL at maximum frown, relative to their pre-treatment appearance, at all post-treatment visits.

Table 1. Global Aesthetic Improvement Scale

Recoded Value	Rating
0	Very Much Improved
1	Much Improved
2	Improved
3	No Change
4	Worse
5	Much Worse
6	Very Much Worse

A responder indicator will be created to identify subjects that experienced an improvement in aesthetic appearance of their GL at maximum frown. If at any given visit the subject selects ‘Improved’, ‘Much Improved’, or ‘Very Much Improved’ on the GAIS, the subject will be considered a Responder at that visit. The subject will be considered a Month 1 Responder only if they are a responder at the month 1 visit.

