2.4.3 Primary analysis

The primary efficacy endpoint will be a responder rate based on the subject GAIS at maximum frown at Month 1 (described in [Section 1.4.1](#)). To evaluate the effectiveness and superiority in aesthetic improvement of QM1114-DP versus placebo in the treatment of moderate to severe GL, the responder rates of QM1114-DP and placebo will be compared using a Cochran-Mantel-Haenszel (CMH) test stratified by site at the 5% significance level (2-sided). The primary efficacy endpoint will be based on the ITT population where missing Month 1 GAIS data will be imputed with 'No Change'.

The null hypothesis of no relationship between treatment and responder rate (i.e., the responder rates are the same in both groups) will be tested against the alternative hypothesis that there is a relationship between treatment and responder rate (i.e., the responder rates are different in the two groups). For a significant result, the two-sided p-value of the comparison of the GAIS responder rate between the QM1114-DP and placebo subjects at Month 1 using the CMH test needs to be smaller than 0.05. For consistency across strata (site), the Breslow-Day test will be used to assess the homogeneity of odds ratios across all sites. If the Breslow-Day test is significant, then the responder rates between the QM1114-DP and Placebo treatment groups will be presented by site.

The estimates of the GAIS responder rates in each treatment group will be presented as well as the difference in responder rates (QM1114-DP responder rate – placebo responder rate). Corresponding 95% CI for the treatment group GAIS responder rates and the difference in responder rates along with the p-value for the difference will also be presented. The normal approximation (Wald) method will be used to calculate both the 95% CI for the individual treatment group GAIS responder rates and the 95% CI for the difference in responder rates. The above responder rates will be presented in figures by visit and treatment group.

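### The multiple-imputation check on the primary endpoint names a GAIS score that is never collected, labels an MAR method as MCAR, omits site, and leaves bounds and rounding undefined in step 2 of a linear model ill-suited to a 7-level scale

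*SAP*

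**What the plan says.** The primary analysis (SAP 2.4.3) sets a missing Month 1 GAIS to No Change and compares responder rates with a CMH test stratified by site. SAP 2.4.2 adds two missing-data checks in the ITT population: multiple imputation, listed first, and observed cases. SAP 2.4.4.1 adds a per-protocol analysis using observed cases.

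The imputation is described in steps:

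- Step 1 uses MCMC to make the missing pattern monotone. It says "The imputation using MI will assume the Missing Completely at Random (MCAR) missing data assumption". Draws below 0 or above 6 are redrawn, and "Imputed values will be rounded to the nearest integer".
- Step 2 fits a linear regression to impute the remaining values. Its covariates are "treatment group and all non-missing GAIS scores from earlier scheduled time points, including baseline". Five imputations are made, and responder status is then derived under SAP 1.3.1. Step 2 does not repeat the bounds or the rounding.
- Each imputed dataset goes through the site-stratified analysis, and the results are pooled.

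Under SAP 1.3.1, subjects rate their lines "relative to their pre-treatment appearance, at all post-treatment visits". Scores of 0, 1 and 2 are responders, and 3 is No Change. Both schedules of assessments mark GAIS from Day 1 onward. Subjects are randomized "in a 3:1 ratio to QM1114-DP or placebo, stratified by site".

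**The concern.** There are four separate faults.

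1. **Baseline covariate.** A rating of change since before the injection has no baseline value, and none is scheduled.
2. **Missing-data assumption.** Regression on treatment and earlier GAIS is valid under MAR. If data really were MCAR, the observed-cases analysis would already be unbiased. As labelled, multiple imputation therefore adds no check under a weaker assumption.
3. **Site.** It stratifies both the randomization and the CMH test but is not in the imputation model.
4. **Model form.** A linear model with one residual variance is applied to a 7-level scale cut between 2 and 3. If placebo subjects cluster at 3 and active subjects spread over 0 to 2, the pooled variance is set mainly by the larger active arm. Responder status then turns on whether draws are rounded: with rounding the cut is 2.5, without it the cut is 2. The SAP does not say which applies in step 2.

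At stake is how far this check can be relied on when the No Change result is judged for robustness.

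**Working it through.** **Inputs from the documents.** Protocol 9.2: "The study is planned to enroll approximately 120 subjects", 90 on QM1114-DP and 30 on placebo. Scale, cut, bounds, covariates and five imputations are as above. Protocol 9.2.1 to 9.2.3 are redacted, so the sample-size calculation cannot be reproduced. The one count that can be recomputed is the number screened (Protocol 5.1): 120 / (1 - 0.10) = 133.3, rounded up to 134, as stated. The SAP gives no figure for the imputation.

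**Assumed.** GAIS distributions giving true placebo responder rates of 3-50% and active rates of 85-98%; 5-20% of Month 1 values missing completely at random. Because missingness is MCAR, any gap between imputed and true rates comes from the imputation model. The variable list is taken to end at Month 1, so missing Month 1 values are filled in step 2.

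**Analytic check, treatment-only model.** For placebo mean m and pooled SD s, the chance of being scored a responder is Phi((c - m)/s), with c = 2.5 if rounded and c = 2 if not. Truncation to 0-6 changes this very little. With an active rate of 98%:

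| True placebo rate | m | s | Rounded | Not rounded |
|---|---|---|---|---|
| 3% | 3.01 | 0.69 | 23% | 7% |
| 10% | 2.93 | 0.71 | 27% | 10% |
| 20% | 2.81 | 0.73 | 34% | 13% |
| 30% | 2.69 | 0.75 | 40% | 18% |
| 50% | 2.45 | 0.77 | 53% | 28% |

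For example, at a true 10%: (2.5 - 2.93)/0.71 = -0.61, and Phi(-0.61) = 0.27.

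**Simulation with the SAP's covariates.** 90:30 subjects, correlated ordinal GAIS on Days 1-4 and Month 1, linear regression on treatment and Day 1-4 GAIS, bounds 0-6, five imputations, 500 runs per scenario, active rate 95%. Imputed placebo responder rates:

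| True placebo rate | Rounded | Not rounded | Binary response imputed by arm |
|---|---|---|---|
| 3% | 21-25% | 5-10% | 4-5% |
| 10% | 26-29% | 9-13% | 11-12% |
| 20% | 33-36% | 13-17% | 20-22% |
| 30% | 39-41% | 18-21% | 30-31% |
| 50% | 51-53% | 28-30% | 49-52% |

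Without rounding, missing active subjects are scored as responders in 85-89% of cases against a true 95%. A separate simulation of the same model gave 24-26%, 26-29% and 34-36% for true placebo rates of 5%, 10% and 20% with rounding. Without rounding it gave active rates of about 82% against 90% and 90% against 95%.

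**Effect on the treatment difference.**

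- Rounded, 10% missing: 0.920 to 0.898 and 0.922 to 0.905 at placebo 3% (-2.2 and -1.7 points); 0.849 to 0.830 and 0.848 to 0.832 at placebo 10% (-1.9 and -1.6). At placebo 30% the shift is -0.9.
- Rounded, 20% missing, placebo 3%: 0.921 to 0.886 (-3.5).
- Not rounded, 10% missing: from -1.5 points (0.920 to 0.905, placebo 3%) to +1.1 (0.448 to 0.459, placebo 50%).
- No Change imputation, 10% missing, placebo 3%: 0.922 to 0.829 (-9.3).
- Binary response imputed by arm: within about 0.5 point of the full-data value.

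In subjects, with 3 of 30 placebo values missing at a true 10%, rounding adds 3 x (0.26 to 0.29 - 0.10) = 0.48 to 0.57 of a responder. Divided by 30, that is 1.6 to 1.9 points.

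The over-scoring comes from the rounded common-variance model. The baseline and MCAR wording do not contribute to it. The effect of omitting site was not simulated and has no fixed direction.

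**The case against.** The case for leaving the plan largely alone is substantial.

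- **It can be run.** A reader might infer that a covariate that does not exist stops step 2. It does not: the SAP asks for non-missing earlier scores, so one never collected drops out and treatment and Day 1-4 GAIS remain. The phrase is an error to delete and does not block the analysis.
- **Over-scoring of placebo is conditional.** A reader might infer that the method always scores too many missing placebo subjects as responders. The documents do not support that: rounding is stated only in step 1, and the placebo distribution is redacted. Without rounding the effect mostly disappears or reverses. With rounding it is nearly gone by a 50% placebo rate. In reply, step 2 derives responders from rating categories and an unrounded 2.3 has none, which favors rounding. Protocol 1.3 expects no clinical benefit on placebo, which favors a low rate. Neither settles the matter, and the unrounded reading has its own bias.
- **The effect is small and confined to a sensitivity analysis.** This stands. With rounding the shift is against QM1114-DP, and No Change imputation lowers the difference much more. Two other prespecified checks do not use this model, so it would be too strong to say that robustness cannot be assessed.
- **MCAR is only a label.** This stands. An MAR-valid method is also valid under MCAR, and no result changes.
- **A full logistic model could be worse.** This stands and shapes the fix. With treatment, site, baseline investigator-rated severity and four GAIS scores, five sites and 10% missing (about 27 observed placebo subjects), a simulation of 300 runs per scenario found complete or quasi-complete separation in 35-59% of trials at 5% placebo response and 14-39% at 10%.

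**Conclusion.** The concern holds as a specification fault in a sensitivity analysis, worth correcting before database lock. The documents themselves establish the uncollected baseline score, the MCAR label on an MAR method, the omission of site, and the silence on bounds and rounding in step 2.

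The size of the bias rests on assumed GAIS distributions. With rounding and a true placebo rate below about 30%, missing placebo subjects are scored as responders too often: about 24-29% at a true 5-10%. Without rounding, missing active subjects fall short by roughly 5-10 points. The model is therefore biased on either reading. At 10% missing and low placebo rates, the rounded version costs about 2 points of treatment difference, against QM1114-DP. The primary result is untouched.

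**What to change.** In SAP 2.4.2:

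1. Delete the reference to a baseline GAIS and state the assumption as MAR.
2. Replace the linear regression, bounds and rounding with direct imputation of Month 1 responder status, or of ordinal GAIS, by logistic regression.
3. Keep the model small: treatment, site (pooled if sparse, as Protocol 9.1.5 allows for the CMH test) and a limited summary of Day 1-4 GAIS. With five sites there are about 30 / 5 = 6 placebo subjects per site.
4. Specify augmented or Firth-type estimation, and a fallback to imputation by arm if separation occurs.
5. Leave the analysis and pooling of the imputed datasets as they are. More than five imputations is optional.

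The cost is minor SAP wording and code, and the covariates are already collected. The drawback is the need to guard against separation in the small placebo arm, which item 4 covers.
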